11.0 TOXICITIES/SIDE EFFECTS

11.1 Adverse Events

An Adverse Event (AE) is any unfavorable and unintended sign, symptom, or disease temporally associated with the use of an investigational medicinal product or other protocol-imposed intervention, regardless of attribution.

This includes the following:

- AEs not previously observed in the patient that emerge during the protocol specified AE reporting period, including signs or symptoms associated with recurrence of melanoma that were not present prior to the AE reporting period.
- Complications that occur during the study as a result of protocol-mandated interventions (e.g., invasive procedures such as biopsies).
- AEs that occur prior to assignment of study treatment that are related to a protocol-mandated intervention (e.g., invasive procedures such as biopsies or medication washouts).
- Preexisting medical conditions that are judged by the investigator to have worsened in severity or frequency or changed in character during the protocol-specified AE reporting period.

11.2 Serious Adverse Event

Serious Adverse Events (SAEs) as defined by the FDA will be recorded and reported as detailed in section 17.2. Recurrent melanoma will not be considered an SAE. However, development of a new primary melanoma will be reported as a SAE.

11.3 Assessment of Adverse Events

All adverse events encountered during the study will be evaluated according to the NC I Common Toxicity Grading system version 4.0. Grade, duration and treatment will be recorded. Life threatening toxicities and serious adverse events should be reported immediately to the Principal Investigator.

11.4 Previously Reported Toxicities Associated with Dabrafenib

The interim results of a phase I/II trial of the dabrafenib in patients with metastatic melanoma and other solid tumors were reported at ASCO in 2010 [15]. Dabrafenib was generally well tolerated with a manageable toxicity profile. The majority of all AEs were reported as Grade 1 and 2. Acute adverse events have been reversible upon discontinuation of dabrafenib and in most instances the drug can be re-started with a dose reduction.

A comprehensive list of the previously reported drug-related toxicities associated with dabrafenib as well as their relative frequencies is presented below. In addition, a more complete discussion will follow regarding a subset of important adverse events with guidelines for management and prevention.

11.4.1 Likely Toxicities (>10%)

- Anemia
- Diarrhea
- Nausea
- Vomiting
- Anorexia
- Constipation
- Rash
- Actinic keratosis
- Hyperkeratosis
- Squamous Cell Carcinoma (SCC) of the skin
- Alopecia
- Pruritus
- Fatigue
- Headaches
- Pyrexia
- Syncope
- Arthralgias
- Myalgias
- Chills

11.4.2 Less Likely Toxicities ($\geq 1\%$ and $< 10\%$)

- Leukopenia and Neutropenia
- Hypophosphatemia
- Abdominal Pain
- Influenza-like Symptoms
- Renal Dysfunction/Acute Renal Failure
- Acrochordon
- Cutaneous papillomas
- Grover's Disease
- Palmar-Plantar Erythrodysesthesia (PPE)
- Uveitis

11.4.3 Rare But Serious ($< 1\%$)

- Pancreatitis
- Drug Hypersensitivity Reactions
- Uveitis/Iritis
- Retinal Vein Occlusion

11.5 Pyrexia

Pyrexia has been observed in several patients on a number of ongoing clinical trials. Fevers have occasionally been associated with hypotension, rigors, renal insufficiency/renal failure, weakness, dizziness, syncope, presyncope, dehydration, nausea, vomiting, and/or an influenza-like illness. Generally, this syndrome is observed within 30 days of initiating dabrafenib. Study participants with pyrexia should be evaluated as detailed in Table 4.

11.6 Acute Renal Failure

Acute renal failure and granulomatous interstitial nephritis have been reported in study participants receiving dabrafenib. In some cases, pyrexia may be associated with renal insufficiency/renal failure, possibly secondary to dehydration or hypotension. Renal function should be monitored carefully, especially in patients with pyrexia. Guidelines for the management of renal dysfunction can be found in Table 7.

11.7 Squamous Cell Carcinoma of the Skin

BRAF inhibition is associated with the development of squamous cell carcinoma (SCC) of the skin, keratoacanthomas (KA) and cutaneous papillomas [39]. The median time to appearance is approximately 8 weeks into treatment. All suspicious lesions should be completely resected by a dermatologist and submitted for pathologic review. A dose reduction is not indicated for this adverse event.

11.8 Ophthalmologic Effects

Ophthalmologic effects including blurred vision (2%), uveitis and iritis ($< 1\%$), eye pain ($< 1\%$), visual impairment ($< 1\%$) and reduced visual acuity ($< 1\%$) have been observed in clinical studies to date, with all events Grade 1 or 2. Retinal vein occlusions have also been reported with RAF inhibitors. An ophthalmologic consult is required for subjects developing symptoms associated with uveitis including blurry vision, eye pain or erythema.

11.9 Reproductive Risk

Preclinical data indicate that dabrafenib is detrimental to the developing fetus. Thus, fertile patients must not become pregnant or father a child while on study. Contraception should be utilized for the duration of the study and for at least 6 months after study completion. Women should not breastfeed while on study.

12.0 CRITERIA FOR THERAPEUTIC RESPONSE/OUTCOME ASSESSMENT

12.1 Assessment of Relapse Free Survival

Relapse free survival is defined as the time from surgical resection to the first recurrence or death as assessed by physical examination and radiographic evaluation. All recurrences will be confirmed by biopsy and histologic evaluation.

12.2 Assessment of Overall Survival

Overall survival is defined as the time from surgical resection to death or last follow-up. Follow up will continue until the completion of the study.

12.3 Assessment of Toxicity

Toxicity will be graded by the NCI Common Toxicity Criteria (CTC) version 4.0 with each cycle of adjuvant dabrafenib.

13.0 CRITERIA FOR REMOVAL FROM STUDY

- Recurrence of the underlying malignancy.
- Unacceptable toxicity not improved with the recommended dose reductions will require cessation of the study drug.
- Development of a secondary malignancy whose systemic treatment would interfere with the study. This does not apply to the development of cutaneous SCC, a known adverse event associated with dabrafenib.
- Development of an intercurrent medical illness in which further administration of the study drug, in the opinion of the Investigator and the treating physician, would be detrimental to the patient.
- Treatment delay of more than 14 days (longer delays must be approved by the Principal Investigator).
- Request of the patient to stop the study.
- Inability of the patient to comply with the requirements of the protocol for treatment or evaluation.

14.0 BIOSTATISTICS

This is a single institution phase II trial assessing the efficacy of adjuvant dabrafenib (GSK2118436) in patients with surgically resected AJCC stage IIIc melanoma characterized by a *BRAF*^{V600E/K} mutation. The primary endpoint is 24 month relapse-free survival rate. Patients will be enrolled within 90 days of surgical resection and monitored clinically and radiographically for relapse for recurrence for 24 months. Data from our Center indicate that the relapse-free survival (RFS) for stage IIIc disease is only 24% at 2 years.

A single stage design will be employed whereby a 24% relapse-free rate at 24 months is considered not promising, a 51% relapse-free rate at 24 months is considered promising, and the probabilities of a type I error (falsely accepting a non-promising therapy) and type II error (falsely rejecting a promising therapy) are set at 0.10 and 0.10, respectively. Twenty-three patients will be accrued. All patients will be followed for a minimum of 24 months. At the end of the trial, if 9 or more patients are relapse-free at 24 months out of a total of 23 patients then the treatment will be considered worthy of further investigation. If 8 or fewer patients are relapse-free at 24 months in then the treatment will be declared negative. The trial would be terminated early if at any time 15 patients relapsed or died before 24 months. This design yields a 0.90 probability of a positive result if the true relapse-free survival is at least 51% and yields a 0.90 probability of a negative result if the true relapse-free survival is 24%.

With the exception of those patients who elect to withdraw consent, all patients will be followed with an intention-to-treat and will be evaluated for the primary endpoint as per the protocol study calendar. This includes patient who develop unacceptable toxicity from the agent, secondary malignancies, or an intercurrent illness as listed in section 13.0. Patients who elect to withdraw consent will be evaluated as follows. If patients relapse on study before withdrawing consent (failure), or if they withdraw consent after month 24 without relapsing (success), they are counted as events. If patients withdraw consent before month 24 and before they relapse, then they are not events and will be replaced. Patients, who are lost to follow up at 24 months or later, are counted as successes and will be censored beyond that point.

Toxicities will be tabulated according to the NCI Common Toxicity version 4.0. Overall survival and relapse-free survival will be estimated using Kaplan-Meier methodology. Overall survival will be assessed from surgical resection to death or last follow-up; relapse-free survival will be assessed from surgical resection to relapse, death or last follow-up. Explorative correlative studies examining the genetic heterogeneity of *BRAF*-mutated melanoma, genetic mechanisms of intrinsic and acquired resistance to dabrafenib, and circulating tumor-derived exosomes as a biomarker of disease recurrence will be reported in a descriptive manner.

A total of 23 patients will be accrued to this study. Enrollment is anticipated to take 6 to 12 months and the study is expected to be completed in 30 to 36 months.

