2.0 OBJECTIVES AND SCIENTIFIC AIMS

2.1 Primary Objective

To determine the RFS at 24 months for patients with Stage IIIC melanoma harboring a *BRAF*^{V600E/K} mutation who are treated with definitive surgical resection followed by four cycles of adjuvant dabrafenib administration.

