3.4 Studyrationale

Preclinical *in vitro* and *in vivo* data with both vemurafenib and dabrafenib indicate that inhibitors of mutated-*BRAF* kinase induce cell death in melanoma cells harboring a *BRAF* mutation [14, 16]. Clinical data demonstrate that inhibition of mutated-*BRAF* kinase results in rapid and significant tumor shrinkage in more than 50% of patients with advanced melanoma characterized by *BRAF*^{V600} mutations independent of disease stage [15, 17-19]. Correlative studies show that apoptosis and tumor necrosis are apparent within one week after the initiation of *BRAF* kinase inhibitors. Anecdotally, we have observed several pathologic complete responses following metastasectomy after best response to *BRAF* kinase inhibition. This indicates that inhibitors of mutated-*BRAF* kinase have the ability to eradicate bulky metastatic disease. It is thus reasonable to speculate that inhibition of mutated-*BRAF* kinase will benefit molecularly selected melanoma patients at earlier stages of the disease.

The underlying hypothesis of this trial is that treatment of micrometastatic disease for 4 cycles will be sufficient to improve RFS in stage IIIC patients with *BRAF* mutations who are currently free of disease. Based on our data at MSKCC [3], stage IIIC patients would be expected to have a RFS of only 24% at 24 months. We will test the hypothesis that 4 cycles of adjuvant dabrafenib will result in an improvement in RFS from 24% to 51% at 24 months.

The duration of treatment (i.e. 4 cycles) was based on the time to maximal response in patients with bulky disease treated with BRAF inhibitor as well as the observation that resistance to these agents generally develops after month six. It was also felt that if continuous adjuvant treatment with dabrafenib were necessary to improve relapse-free survival, then treatment at relapse would likely be just as effective and the rationale for adjuvant therapy would be undercut.

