6.0 CRITERIA FOR SUBJECT ELIGIBILITY

6.1 Subject Inclusion Criteria

- 6.1.1 AJCC (2009) stage IIIC cutaneous melanoma rendered free of disease by surgical resection no greater than 90 days prior study enrollment. Patients with unknown primaries will be eligible for this trial. Patients with a history of resected stage I or II cutaneous melanoma who subsequently have their first disease recurrence meeting the criteria for stage IIIC disease will also be eligible for this trial.
- 6.1.2 Patients must have clear margins after wide local excision. Patients with nodes that are palpable or detectable on radiologic imaging must have an adequate lymphadenectomy.
- 6.1.3 Patients must be adequately recovered from surgery, radiation therapy, or any surgical complications prior to enrollment. In general, this means patients will be off antibiotics from wound infections and drains removed. However, if necessary, patients can be treated with a drain in place at the discretion of the PI if the 90 days window is about to expire.
- 6.1.4 Histologic proof of melanoma reviewed and confirmed by MSKCC.
- 6.1.5 A documented *BRAF*^{V600E} or *BRAF*^{V600K} mutation by genotyping or IHC [35] performed by a CLIA certified laboratory.
- 6.1.6 Age \geq 16 years old.
- 6.1.7 ECOG performance status = 0 or Karnofsky Performance Status equivalent (Appendix A).
- 6.1.8 The ability to swallow pills.
- 6.1.9 Patients must have adequate organ and marrow function as defined below:

Absolute neutrophil count	≥ 1.5 K/mcL
Platelets	≥ 100 K/mcL
Hemoglobin	≥ 9.0 g/dL
Total bilirubin	≤ 1.5 X institutional upper limit of normal (ULN) ≤ 3.0 X institutional ULN if the patient has Gilbert's Syndrome
AST (SGOT) and ALT (SGPT)	≤ 2.5 X institutional ULN
Creatinine	≤ 1.5 X institutional ULN or creatinine clearance (calculated or measured) > 60 ml/min

6.1.10 Women with child bearing potential and men with reproductive potential must be willing to practice acceptable methods of contraception.

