8.4 Within 2 weeks of the start of the study

- Updated medical history and physical examination
- A complete skin examination by dermatology or a consenting medical oncologist.
- An eye examination by ophthalmology
- Laboratory studies including a CBC with differential; comprehensive metabolic panel; serum phosphorous, magnesium and LDH levels.

- A serum pregnancy test for woman of child-bearing potential.
- Appropriate radiologic assessment to assure no evidence of disease. In general, this will involve a CT scan (with contrast) of the chest, abdomen and pelvis; if the patient is not able to undergo a CT scan, a MRI with and without gadolinium may be used. For patients with a primary melanoma below the knee, a PET scan with a non-contrast chest CT will also be acceptable.

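### The 24% null carries no stated match to the trial's delayed, disease-free entry; if it is unconditional from surgery, selection raises the type I error of the 9-of-23 rule above 0.078, possibly past 0.10

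*Combined protocol and SAP*

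**What the plan says.** Section 12.1 and the Kaplan-Meier paragraph of Section 14.0 both start the RFS clock at surgical resection and count relapse or death. Section 10.1 ends active follow-up 24 months after resection.

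Entry comes later. Section 14.0 states: "Patients will be enrolled within 90 days of surgical resection and monitored clinically and radiographically for relapse for recurrence for 24 months". Section 6.1 admits patients "rendered free of disease by surgical resection no greater than 90 days prior study enrollment". Section 8.4 asks, within 2 weeks of study start, for "Appropriate radiologic assessment to assure no evidence of disease". Brain imaging has a wider window of 4 weeks (Section 8.3), and Table 8 schedules none again until the 24-month visit. Entry late in the 90 days is foreseen: Section 8.2 allows adjuvant radiotherapy to be completed first, and Section 6.1 provides for patients whose window is about to close.

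The null comes from one sentence in Section 14.0: "Data from our Center indicate that the relapse-free survival (RFS) for stage IIIc disease is only 24% at 2 years". Section 3.4 puts it as "stage IIIC patients would be expected to have a RFS of only 24% at 24 months", just after describing the target population as patients with BRAF "mutations who are currently free of disease". Neither place gives the time origin, the event definition or any entry condition of the Center figure. Section 14.0 then claims that the design "yields a 0.90 probability of a negative result if the true relapse-free survival is 24" per cent.

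**The concern.** A patient who dies, or whose relapse is found, between surgery and entry cannot be enrolled. Every enrolled patient is nevertheless credited with that interval as relapse-free time. If the Center's 24% counts all resected stage IIIC patients from the day of surgery, it includes early failures that the trial screens out. The 24-month success rate of enrolled patients on an inert drug would then be higher than 24%.

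In a single-arm trial the null rate is the whole control. A null set too low makes 9 or more successes easier to reach without any drug effect. The reader cannot tell whether the claimed 0.90 probability of a negative result applies to the patients who will actually be enrolled.

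**Working it through.** **Inputs.** From Section 14.0: n = 23, positive if 9 or more are relapse-free, p0 = 0.24, p1 = 0.51, both error rates set at 0.10. From Sections 6.1 and 8.4: entry up to 90 days after surgery, body imaging up to 2 weeks before study start. The documents give neither the early failure rate nor the distribution of entry times; both are assumed below.

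**Step 1: reproduce the design.** With X binomial(23, p):

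- P(X ≥ 9 | 0.24) = 0.0776, so the probability of a negative result is 0.922.
- P(X ≥ 9 | 0.51) = 0.911.

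Both stated limits are met. Stopping at 15 failures leaves at most 8 successes, so the early-termination rule changes neither figure.

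**Step 2: break-even.** Let q be the share of comparable patients who relapse or die before entry. If 24% is unconditional from surgery, the null among those enrolled is p0' = 0.24/(1 − q). Solving P(X ≥ 9 | p0') = 0.10 gives p0' = 0.2518, so q = 1 − 0.24/0.2518 = 4.7%. If 24% is a rounded value, 0.235 gives q = 6.7% and 0.245 gives q = 2.7%.

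| q | p0' | Type I error |
|---|---|---|
| 3% | 0.247 | 0.091 |
| 5% | 0.253 | 0.102 |
| 10% | 0.267 | 0.133 |
| 15% | 0.282 | 0.175 |

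**Step 3: scenarios for q (assumed).** Take H = −ln(0.24)/24 = 0.0595 per month, a multiple m of that hazard before entry, and p0' = 0.24·exp(m·H·gap). Entry is uniform over 0 to 3 months and p0' is averaged over it. The lag column shortens each gap by 14 days (0.46 month, floor 0), because a relapse after the screening scan does not bar entry and later counts as a failure.

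| m | Mean p0' | Type I error | With full 2-week scan lag |
|---|---|---|---|
| 1 | 0.263 | 0.124 | 0.109 |
| 0.5 | 0.251 | 0.098 | 0.092 |
| 0.25 | 0.245 | 0.087 | 0.085 |

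The error crosses 0.10 at m = 0.53 without lag and m = 0.74 with it. Two weeks is not the upper bound for brain relapse, where the scan may be 4 weeks old and is not scheduled again until 24 months.

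**Step 4: single landmarks (same hazard assumption, no lag).**

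| m | 30 days | 60 days | 90 days |
|---|---|---|---|
| 1 | 0.106 | 0.141 | 0.186 |
| 0.5 | 0.091 | 0.106 | 0.122 |
| 0.25 | 0.084 | 0.091 | 0.098 |

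**Step 5: power.** Applying the implied hazard ratio, ln(0.51)/ln(0.24) = 0.472, to the conditional nulls of Step 3 (no lag) gives p1 between 0.515 and 0.532 and power between 0.920 and 0.941. Power is not at risk.

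**Step 6: the Center's own figures.** Section 3.1 reports 5-year RFS of 15% and 5-year overall survival of 11%, citing the reference that Section 3.4 uses for the 24%. Under the Section 12.1 definition every death ends RFS, so RFS cannot exceed overall survival in one cohort from one origin. At least one of these figures therefore uses another event definition, origin or cohort, or is misreported.

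**The case against.** The strongest reply is that the excess depends on a source the documents do not describe. If the Center series was already limited to patients disease-free at a similar point after surgery, the shift shrinks or vanishes, and Section 3.4 does apply the figure to patients free of disease. This stands as a limit on the claim. It does not close the question: Section 3.4 shows whom the figure is meant for, not how it was calculated.

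The bias may also run the other way. If the Center's RFS did not count all deaths, the null under Section 12.1 would be below 24%. As an assumed illustration, a base of 22% with 10% early failures gives p0' = 0.22/0.90 = 0.244 and a type I error of 0.086. The trial's scans every 3 months could likewise record more failures by 24 months than a less closely imaged series; the documents do not say how that series was imaged. Both possibilities stand.

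The threshold is also not sharp: rounding alone moves it from 2.7% to 6.7%, and at half the constant hazard with uniform entry the error stays at 0.098.

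A reader might infer that the design is miscalculated, or that the trial does exceed 0.10. The documents support neither. Section 14.0 is right, and somewhat conservative, at a true 24%, and no early failure rate is given. Nor does the 15% against 11% discrepancy show which way the benchmark errs; it shows only that its definition cannot be taken for granted.

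**Conclusion.** The mismatch is documented: a clock from surgery, entry up to 90 days later on disease-free imaging, and a null with no matching condition. Its effect on the type I error is conditional. If the 24% is unconditional from surgery and counts events as Section 12.1 does, the true error of the 9-of-23 rule lies above 0.078 and passes 0.10 at about 4.7% early failures. The assumed uniform-entry scenarios give about 0.087 to 0.124 before scan lag, so the likely size is modest. An offset from the benchmark's event definition is possible. This is worth fixing because the benchmark is the only control and the Center can check it from its own data, but a breach of 0.10 has not been shown. Confidence is medium.

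**What to change.** In Section 14.0:

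- State the time origin, event definition and entry condition of the 24%.
- Re-derive it from the Center's data with the Section 12.1 definition (relapse or death, from surgery) among patients still disease-free at prespecified landmarks of 30, 60 and 90 days after resection.
- Reconcile the 5-year RFS and overall survival figures in Section 3.1.
- Keep n = 23 and the cut-off of 9. Restate p0 and the attained type I error at the conditional null, as a range over the three landmarks. At or below 25.2% the stated 0.10 stands.
- Report the distribution of surgery-to-enrolment gaps, and note that the RFS estimate is conditional on being disease-free at entry.

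Fixing the landmarks in advance keeps the null independent of the trial's own entry times. Weighting by observed gaps or adding a delayed-entry curve is optional.

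The cost is a small in-house re-analysis and a text amendment, with no added patients or visits and no change of decision rule. The downside is that the stated type I error may become slightly less favourable.

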15.0 RESEARCH PARTICIPANT REGISTRATION AND RANDOMIZATION PROCEDURES

15.1 Research Participant Registration

Confirm eligibility as defined in the section entitled Criteria for Patient/Subject Eligibility.

Obtain informed consent, by following procedures defined in section entitled Informed Consent Procedures.

During the registration process registering individuals will be required to complete a protocol specific Eligibility Checklist.

All participants must be registered through the Protocol Participant Registration (PPR) Office at Memorial Sloan-Kettering Cancer Center. PPR is available Monday through Friday from 8:30am – 5:30pm at [contact]. Registrations must be submitted via the PPR Electronic Registration System (<http://ppr/>). The completed signature page of the written consent/RA or verbal script/RA, a completed Eligibility Checklist and other relevant documents must be uploaded via the PPR Electronic Registration System.

